5. IMPACT EVALUATION (IE)

5.1. Aims, Objectives and Hypotheses

Aims and Objectives

The IE aims to estimate the impact of LAs delivering proactive support to households deemed at risk of homelessness in the next 3-6 months on whether they are owed a relief duty.

The **primary objective** of the IE is to estimate the impact of treatment on whether households are owed a relief duty at a 9-month follow-up.

The **secondary objective** is to estimate the impact of treatment on support provided for at-risk households before the 9-month follow-up.

Research hypotheses

The **primary research hypothesis** is that allocation to treatment will reduce the likelihood of a household making a homelessness application that results in them being owed a relief duty at any point between the trial's start and the 9-month follow-up, compared to a business-as-usual (BAU) control. See 'Primary Outcome', below for the operational definition used in this trial.

The **secondary research hypotheses** are that allocation to treatment will increase the likelihood of anyone in the household being issued the following support before the 9-month follow-up:

1. A prevention duty ('Primary Outcome', below)
2. An agreed reduction in Council Tax
3. A discretionary housing payment

The trial will also consider impact on these three secondary outcomes at an earlier 2-month follow-up.

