7.2. Secondary Outcomes

The trial's secondary outcomes are focused on evidence of more proximate impact of treatment on support delivered by LAs to at-risk households. Our three (binary) secondary outcome measures of support are listed below. We will consider each at

the end of the trial (i.e., the 9-month follow-up) but also at an earlier 2-month follow-up to produce evidence of early impact on an interim basis.

Secondary outcome 1: 'Prevention Duty'

Definition

Whether a [prevention duty](#) was issued to the household or any household members (1) or not (0).

Why is it measured

To indicate whether the intervention leads to increased preventative action taken by LAs, either as a result of the call making households' need for support apparent to LAs or by resulting in earlier access to support.

Data source

Aggregated from Homelessness Case Level Information Classification ('H-CLIC') records, via the OneView platform.

When is it measured

At the 9- and 2-month follow-ups.

For whom is it measured

All households enrolled in the trial.

Secondary outcome 2: 'Council tax reduction agreement' (assuming that Xantura will be able to make this data available to us)

Definition

Whether a Council Tax reduction has been agreed for the household (1) or not (0).

Why is it measured

To indicate whether the intervention leads to improved debt management support to keep at-risk households in their current accommodation.

Data source

SHBE (Single Housing Benefit Extract) data held by LAs, via the OneView platform.

When is it measured

At the 9- and 2-month follow-ups.

For whom is it measured

All households enrolled in the trial.

Secondary outcome 3: 'Discretionary Housing Payment'

Definition

Whether a Discretionary Housing Payment was issued to any household members (1) or not (0). A discretionary housing payment is a payment designed to cover housing costs for a rent shortfall, rent deposits, or to pay rent in advance if the individual needs to move home. To be eligible, individuals must receive either Housing Benefit or the housing element of Universal Credit.

Why is it measured

To indicate whether the intervention leads to improved financial support to keep at-risk households in their current accommodation.

Data source

Revenues and Benefits records held by LAs, via the OneView platform.

When is it measured

At the 9- and 2-month follow-ups.

For whom is it measured

All households enrolled in the trial.

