These costs are expected to accrue directly to the LAs participating in the project. However, given the project's RCT implementation structure, each LA will be providing services simultaneously to the intervention and control groups – whilst funding them through a range of sources, including:

- Unitary/Lower-tier LA own budget
- Upper-tier LA funding
- MHCLG Rough Sleeping Initiative grants,⁵ a multi-year programme providing local councils with long-term funding to support those sleeping rough or at risk of rough sleeping
- Other central government funding.

Therefore, it would not be practical to differentiate between the intervention and BAU delivery costs according to their funding source. Instead, we recommend that these costs are assessed based on spending data collected from the participating LAs through the dedicated Cost Data Submission Tool.

The table below provides further detail on the spending categories to be considered as part of the Cost Data Submission Tool.

Table 9: Economic Evaluation costs

Cost	Supplementary Data Source	Notes
Intervention only		
Direct costs OneView platform license fee (market value) LA resources (salaries, time, overheads, fees) spent on: Setup, monitoring and maintenance of OneView data Call handler training Casework (intervention phone calls providing proactive support) Administration of intervention	Cost Data Submission Tool*	
Intervention and counterfactual		

⁵ [Rough Sleeping Initiative: 2022 to 2025 funding allocations](#)

Indirect costs LA resources (salaries, time, overheads, fees) spent on: Running cost of existing support services	Cost Data Submission Tool* Can be triangulated against relevant Simetrica-Jacobs exchequer values ⁶ estimated for the HACT UKSVB ⁷	To be apportioned according to service uptake in intervention and control groups ⁸
--	---	---

** LAs will be provided with a comprehensive **cost** form to populate. A copy of the Cost Data Submission Tool will be provided separately.*

Benefits (and averted costs)

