The intervention aims to benefit society by reducing the number of at-risk households whose members are owed a relief duty because they have become homeless. We will capture the value of these benefits through proxy measures that focus on the resulting financial implications for the LAs and the central government, such as avoided spending on temporary accommodation and reductions in Council Tax debt, or the averted costs of housing support, healthcare expenditure and unemployment benefit payments. These proxy measures effectively represent resources that become freed up thanks to the intervention, and that can be invested to create social value for others in society.

We will estimate cost savings resulting from the intervention in relation to the following key outcomes:

- Reduced need for temporary accommodation
- Reduced Council Tax debt
- Reduced Council housing rent arrears
- Reduced need for emergency relief services

⁶ E.g. provision of housing, financial and debt advice.

⁷ The HACT UKSVB exchequer values have been developed by piecing together various sources of evidence linking outcomes such as housing quality, employment or health to data on public expenditure. It is an approach that relies on a range of judgements and assumptions that allow the quantification of an outcome's financial implications for the government, such as increased tax revenue and cost savings from reduced healthcare expenditure. Details of these assumptions will be provided alongside the relevant monetary values applicable to this evaluation.

⁸ Subject to availability of data on the relevant uptake rates; our understanding is that this may vary depending on the type of support service – e.g. data on the use of Council-run services around debt/Council Tax are likely to be available through the OneView platform, but data on the use of third-party services would be more difficult to obtain.

- Increased financial support to gain/maintain secure housing in the social rented sector
- Increased financial support to gain/maintain secure housing in the private rented sector
- Avoided loss of full-time employment
- Avoided deterioration in overall health

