Council tax arrears	Xantura predictive model data – based on LA Council Tax arrears records, split by intervention and control group	Reduced Council Tax debt
Council housing rent arrears	Xantura predictive model data – based on LA records on Council housing rent arrears, split by intervention and control group	Reduced Council housing arrears
Emergency relief services annual budget	https://www.mannasociety.org.uk/ within Crisis report (2016), p.26 ¹⁰	Reduced need for emergency relief services ¹¹
Average weekly (social and affordable) rent (2022/23)	Live tables on rents, lettings and tenancies 2022/23, MHCLG	Increased financial support to gain/maintain secure housing in the social rented sector
Government expenditure on housing element of Universal Credit (GB) (2022/2023)	Benefit expenditure by country and region, 1996/97 to 2022/23, DWP	Increased financial support to gain/maintain secure housing in the private rented sector
Cost of unemployment benefits	Based on Simetrica-Jacobs' exchequer values estimated for the HACT UKSVB	Avoided loss of full-time employment

¹⁰ The report uses the annual cost data, which is published by a day centre in London, seeing between 150-180 single homeless people per day and with an annual budget amount reported.

¹¹ This may not constitute a cost to the public sector if the services are provided e.g. by a housing association.

Cost of NHS services for those in poor overall health	Based on Simetrica-Jacobs' exchequer values estimated for the HACT UKSVB	Avoided deterioration in overall health
---	--	---

Note: The outcome-level estimates considered above will be triangulated against other existing estimates of the overall costs of a homelessness application, e.g. from the GMCA Unit Cost Database or the upcoming research from LSE/MHCLG.

Sensitivity Analyses

Sensitivity analysis will aim to reflect the level of estimation uncertainty around key components of the economic evaluation calculations, including (where relevant):

- Number of beneficiary households – e.g. using confidence intervals around the central impact estimates from the impact evaluation
- Cost of delivering the intervention – e.g. using a high-low range of additional intervention implementation costs to the LAs, depending on the variation in responses to the Cost Data Submission Tool (see more details in section 12.3)

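### The economic evaluation credits lower Council Tax and rent arrears as savings but has no cost line for the Council Tax reductions and discretionary housing payments the trial hypothesises will rise, so net value would be overstated if they do

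*Protocol*

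**What the plan says.** Protocol section 5.1 states the secondary hypotheses as "allocation to treatment will increase the likelihood of anyone in the household being issued the following support before the 9-month follow-up". Two of the three items listed are "An agreed reduction in Council Tax" and "A discretionary housing payment". Section 7.2 makes clear that the second is money, not staff time: "A discretionary housing payment is a payment designed to cover housing costs for a rent shortfall, rent deposits, or to pay rent in advance".

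Section 12.2 sets out the two sides of the economic account.

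- **Costs.** The text lists the licence fee, LA staff time for set-up and maintenance, the calls, and indirect LA support costs. Table 9 gives the indirect line, for both arms, as "LA resources (salaries, time, overheads, fees) spent on: Running cost of existing support services". The protocol introduces Table 9 as the detail of the spending categories in the Cost Data Submission Tool.
- **Savings.** The listed outcomes include "Reduced Council Tax debt" and "Reduced Council housing rent arrears". Table 10 sources the first from model data "based on LA Council Tax arrears records, split by intervention and control group", and describes the council rent arrears source in the same way.

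The value-for-money test in section 12.2 requires the intervention to cut public spending by more than it cost to deliver. Section 12.1 adds a second perspective, that of the LA alone.

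**The concern.** A Council Tax reduction is revenue that the LA gives up, and a discretionary housing payment is public cash paid out. Either can lower a household's recorded arrears. The plan then counts the fall in arrears as a gain, while the award that produced it is recorded nowhere. Arrears that fall because a bill was reduced, or because public money paid the rent, have not freed public resources by that amount.

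The omission works in the intervention's favour, and it grows with success on secondary outcomes 2 and 3. It bears on the net value per beneficiary household, on the comparison with the break-even benchmark, and on the comparison with other programme initiatives. Section 12.1 says individual LAs are likely to make the adoption decisions, so the LA-perspective result matters. The primary outcome and its analysis are not affected.

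**Working it through.** **1. Is there a figure to reproduce?** No. The protocol states no net value, unit cost, award amount or award rate. The one protocol figure used below for scale is the minimum detectable effect of 2 to 7 percentage points (section 9.1; Table 7, Scenario C). With 800 analysed per arm, a two-proportion calculation gives about 2.0 points at a 3% base rate and 7.0 points at 50%, which agrees.

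**2. Lines set side by side.**

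| Item | Hypothesised direction (5.1) | Cost line in Table 9 | Line in Table 10 |
|---|---|---|---|
| Council Tax reduction, £ value | up | none | none |
| Discretionary housing payment, £ value | up | none | none |
| Council Tax arrears | not a hypothesis | not applicable | credited as saving |
| Council rent arrears | not a hypothesis | not applicable | credited as saving |

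The two Table 10 rows on increased financial support for housing are sourced from average social and affordable rents and from spending on the housing element of Universal Credit. Neither source measures these awards.

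**3. Accounting for one extra award of £X.** This takes the plan's own convention that £1 of arrears is £1 lost, and the public-sector perspective.

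- *Award clears £X of arrears that are credited as a saving.* The plan books +X and no cost. The true net is about 0, so the overstatement is X.
- *Award clears no credited arrears, such as a payment to a private tenant.* The plan books 0. The true net is −X, so the overstatement is again X.

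In both cases the error is X once. Adding the omitted cost to the arrears saving would give 2X, which is wrong.

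**4. Testing the remedy on the first case.**

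- Award entered as a cost, arrears saving left gross: X − X = 0, as it should be.
- Award entered as a cost and also netted from arrears: (X − X) − X = −X, which understates net value.

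**5. Assumed illustration of scale.** Inputs:

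- N = 1,000 treated households (Table 7, Scenario C)
- Δa = 2 to 10 percentage points more awards (assumed)
- m = £250 to £2,000 mean award (assumed)
- Δr = 2 to 7 percentage points fewer relief duties (the minimum detectable effect range, used only for scale)

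Total uncosted awards = N × Δa × m:

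- low: 1,000 × 0.02 × £250 = £5,000
- high: 1,000 × 0.10 × £2,000 = £200,000

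Per beneficiary household = (Δa ÷ Δr) × m:

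- low: (0.02 ÷ 0.07) × £250 ≈ £71
- high: (0.10 ÷ 0.02) × £2,000 = £10,000

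The ratio Δa ÷ Δr runs from 0.29 to 5. It can exceed 1 because awards also go to treated households that are not beneficiary households. With Δa = 0 the omitted cost is zero.

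**6. The arrears saving on the same assumptions.** Section 12.2 applies savings to beneficiary households or their members, not to everyone treated. If the award-driven arm difference (Δa × m, £5 to £200 per household) serves as the unit value, and beneficiaries number 1,000 × Δr = 20 to 70, the saving booked is £5 × 20 = £100 to £200 × 70 = £14,000. So it need not be of the same order as the uncosted awards.

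**The case against.** The best defence is that the plan's wording already reaches these awards. Section 12.1 describes indirect costs broadly, as the cost of support taken up through signposting. Sections 2.1 and 7.2 treat both awards as support delivered by LAs, and section 1.1 mentions discretionary housing payments among the services used in the earlier pilot. The Cost Data Submission Tool is provided separately and might hold a field for them. A discretionary housing payment could also be placed under the financial-support outcomes, and section 12.2 promises to reflect items that balance out across public bodies.

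This does not close the gap. Table 9 is presented as the detail of the tool's categories, and it narrows indirect costs to staff, overheads and fees for running services. The financial-support rows are valued from other sources. The balancing text concerns offsets between different public bodies, whereas a Council Tax reduction and the matching fall in Council Tax debt both sit with the same LA.

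Several limits do stand. A reader might infer that net value is overstated outright, but that depends on awards rising, which is a hypothesis. A reader might also infer that a false saving as large as the uncosted awards comes on top of them. The documents do not support this: savings are applied to beneficiary households, and the two amounts overlap. The offset against rent arrears concerns council tenants only, although an uncosted payment is a missing public cost in any tenure. The protocol does not say who funds discretionary housing payments, so an effect on the LA perspective is clear only for Council Tax reductions.

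**Conclusion.** The omission is real. The value of the two awards is in neither table, while the arrears they can reduce are credited as savings. Followed as written, the plan would overstate net value and flatter the break-even comparison if awards rise as hypothesised. The direction follows from the trial's own secondary hypotheses. The size cannot be derived from the documents: £5,000 to £200,000 in total, or about £71 to £10,000 per beneficiary household, rests on assumed award rates and amounts, and on the minimum detectable effect range standing in for the true effect. This should be corrected before the economic analysis is run.

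**What to change.** Add to the part of Table 9 that covers both intervention and counterfactual the £ value of Council Tax reductions and of discretionary housing payments awarded, by arm and across all randomised households. Attribute each to the public body that bears it, so that the public-sector and LA perspectives each carry the right share.

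Count each award once. With the award entered as a cost, leave the arrears savings in Table 10 gross and do not also net the award from them. State in Table 10 which households the arrears difference is applied to, so that the overlap with the awards can be seen. If the Cost Data Submission Tool already collects award values, one sentence saying so and an amended Table 9 would be enough.

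The cost is obtaining award amounts, not just yes/no indicators, from the benefit records used for secondary outcomes 2 and 3. For Council Tax reductions this is subject to the caveat in section 7.2 that even the indicator depends on Xantura being able to supply the data. No new contact with participants is needed. The reported net value may be less favourable.

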12.3. Data Collection and Processing

Data Sources

We will collect data on the intervention costs from the LAs through a Cost Data Submission Tool and triangulate these – where relevant and applicable – with appropriate external data sources. The study's impact evaluation will provide estimates of the number of beneficiary households (households whose members avoid being owed a relief duty because they have become homeless) required for the estimation of cost savings resulting from the intervention.

Data Collection Procedures

A Cost Data Submission Tool in the format of an Excel file will be developed by Simetrica-Jacobs. This will be distributed to the LAs participating in the project as part of the IPE's qualitative data collection process (TBC).

The cost estimates obtained from returned submissions forms will be scaled up in line with the project target population in each LA to represent the whole project.

Data Collection Schedule

- Cost data submission form developed – 30th September 2024 (Simetrica-Jacobs)
- Cost data submission form sign-off – 30th October 2024 (CHI/consultation with LAs - TBC)
- Cost data submission form distribution – TBC

12.4. Analysis

We will implement the VfM calculations in an Excel spreadsheet format. This document will consist of separate tabs with the following information:

- Unit values – a list of monetary values to be applied in the VfM calculation, specifying the source of the value and the relevant units (e.g. per household / per person),
- Inputs – intervention parameters feeding into the VfM calculation, including the intervention impact estimates from the impact evaluation, intervention costs reported through the Cost Data Submission Templates, and the relevant population size,
- Assumptions required for the VfM calculation, including the cost savings probabilities (for each outcome/value) per beneficiary household, evaluation time horizon, price uprating, discounting, optimism bias, etc.
- VfM Calculation – main tab combining the information on unit values, inputs and assumptions to calculate the present value of the intervention costs and cost savings
- Outputs – a summary of the intervention overall net present value per beneficiary household, intervention cost efficiency ratio and benchmark cost

efficiency ratio. This tab will also present variants of the results under selected sensitivity analysis scenarios.

The development of the Excel spreadsheet will be subject to an internal Simetrica-Jacobs quality assurance process, embedded in the design of our management structure to ensure clear lines of accountability and sufficient resourcing to ensure all steps of the calculation are reviewed by a Simetrica-Jacobs team member not involved directly in the project delivery. The finalised spreadsheet can be provided as an annex to the written evaluation findings.

13. QUALITY CONTROL AND ASSURANCE

13.1. Data Quality and Assurance

Quantitative data impact evaluation data will be collected by Xantura and will be subject to their quality controls and assurance processes. Analysis of quantitative and qualitative data will be done by Verian and will be subject to their internal quality assurance processes, with code being quality assured, as well as analytical decisions discussed among the evaluation team.

The randomisation will be carried out by a researcher of Research Manager grade or higher, who will hold either a Masters degree in statistics or a PhD in a quantitative research field. A senior researcher (Director or Senior Director grade) will review the randomisation code and check the resulting sample file for transcription errors, as well as carrying out balancing checks on key covariates. We will follow the same process for quality assuring all inferential analyses, with additional spot checks on headline descriptive statistics. The senior researcher will document sign-off on the randomisation and analysis.

13.2. Protocol Deviations and Non-Compliance

All deviations from the trial protocol will be recorded in a deviations log associated with the trial. This will include non-adherence to randomisation, deviations in the data collection, changes to the eligibility criteria, and any changes to the analysis necessitated by unforeseen circumstances. This deviations log will be shared between Verian, LAs, and CHI, and will be updated by all organisations as deviations occur. Prior to analysis taking place, the evaluation team will consider these deviations and whether they necessitate changes to the analysis. If they do, a protocol addendum will be written by the evaluators and reviewed by CHI prior to publication, and prior to any analysis taking place. This follows the process laid out by (Anders et al., 2022) for evaluations of complex interventions. The full (anonymised) deviations log will be published as an appendix to the final evaluation report.

